Proprietary and Confidential

BOMARIN 270-201 Amendment 10

^a Brief physical examination should be done at all weekly visits except Week 16, where a complete physical examination should be performed. Refer to Section 9.7.9.5. ^bRefer to Table 9.7.9.2.1 for laboratory assessments to be included, and to Table 9.7.9.3.1 for liver tests. LTs may be monitored more or less frequently (and in particular when ALT values are >1.5x ULN) based on discussion between the Medical Monitor and the Investigator and review of subject data, but LTs will be monitored at least twice weekly during periods when a subject's ALT is \geq 3x ULN. Patients with ALT > 1.5 ULN during the study may undergo additional evaluations (eg, imaging studies including MRI or ultrasound, additional blood tests, and/or liver biopsy) at the discretion of the investigator. Additional testing of FVIII and LTs during any study week may be performed if: (1) the ALT has increased to above ULN; (2) Increases in ALT values from prior assessment are accompanied by declines in FVIII activity level; or after a discussion between the Medical Monitor and the Investigator based on a review of subject data. If FVIII levels and/or ALT values are stable over the course of several weeks, assessment of FVIII activity and ALT levels may be adjusted based on discussion between the Medical Monitor and the Investigator. ^c Includes hFVIII activity level (one-stage clotting assay and chromogenic substrate assay). If a subject has used FVIII within 72 hours of a measurement day, all efforts should be made to obtain FVIII activity measurements when a 72-hour interval without FVIII use is achieved; the 72-hour wash-out period is only intended for subjects who have achieved FVIII \geq 5 IU/dL at 16 weeks after BMN 270 infusion and who have not resumed standard of care FVIII replacement therapy. If FVIII levels are elevated or stable over the course of several weeks, assessment of FVIII activity may be adjusted based on discussion between the Medical Monitor and the Investigator. A d-dimer may be considered under circumstances in which FVIII activity levels are above the normal physiological range and/or if there is a concern for a venous thromboembolism.

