^a Reactive corticosteroids may be initiated when a subject's ALT value is \geq 1.5x ULN or based on review of FVIII and liver enzyme data after consultation between the Investigator and the Medical Monitor.

^b Following initiation or completion of steroid regimen, if ALT elevation $\geq 1.5x$ ULN is reported, steroid management decisions will based on discussions between the Investigator and Medical Monitor. Modification of the steroid regimen may take into consideration timing of the ALT elevation (after Week 52), as well as possible confounders for the ALT elevation and adverse events related to corticosteroid dosing. Guidance for tapering oral corticosteroids can be found in Section 9.4.8.2.

^c After discontinuation of corticosteroids, weekly labs for ALT and FVIII levels will be measured once a week for 4 weeks to ensure stability in values. If these assessments are already being done as part of normal study follow-up, they do not need to be duplicated.

^d Regardless of the assessments listed in the Schedule of Assessments (Table 9.1.2, Table 9.1.3, or Table 9.1.4), subjects initiated on corticosteroids will only be required to have laboratory evaluations on a weekly basis.

^e Should only be performed in subjects with a history of hepatitis B or hepatitis C prior to study entry.

270-201 Amendment 10

Table 9.1.7: Schedule of Events – Liver Biopsy Substudy

	Within 28 Days Before Biopsy Day	Within 7 Days Before Biopsy Day	1 Day Before Biopsy Day ^d	Biopsy Day (BD)
Informed Consent	X			
Liver Ultrasound ^a	X			
Brief Physical Examination	X		X	Х
Hematology, Coagulation, Chemistry Assessments ^b	X		X	
Liver Tests ^b	X		X	Х
FibroScan		Х		
Local FVIII Activity Level Assessment		Х	X	Х
Pre-Biopsy Consultation ^c		Х		
Liver Biopsy ^e				Х

^a Liver ultrasound must be performed within 28 days prior to the scheduled biopsy, unless an ultrasound result from the prior 3 months is already available.

^b Refer to Table 9.7.9.2.1 for laboratory assessments to be included, and to Table 9.7.9.3.1 for liver tests.

^c Subjects will undergo a pre-biopsy consultation with the investigator (treating hematologist).

^d Subjects may need to repeat/extend this visit if their FVIII activity levels need adjustment before the biopsy, at the discretion of the investigator (treating hematologist).

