9.4.8.2.1 Reactive Corticosteroids

In general, reactive corticosteroids may be initiated when a subject's ALT value is $\geq 1.5x$ ULN, or based on review of FVIII and liver enzyme data after consultation between the Medical Monitor and the Investigator. Corticosteroids may be delayed, upon discussion with the Medical Monitor, if elevations in ALT are clearly not related to BMN 270 (eg, elevated ALT with concurrent increase in CPK due to intensive exercise) and in particular for elevations occurring more than 52 weeks after BMN 270 dosing.

BIOMARIN[®] 270-20

270-201 Amendment 10

Page 63

Reports of raised LTs (defined as $ALT \ge 1.5x$ ULN) should be made to the BioMarin medical monitor within 30 minutes of the lab value being available. Local laboratory results of LTs will be used to trigger corticosteroid treatment as needed. In case of discrepant results between local and central laboratories, the Investigator and Medical Monitor will decide further action.

Following initiation or completion of reactive corticosteroids, if ALT elevation \geq 1.5x ULN is reported, steroid management decisions will based on discussions between the Investigator and Medical Monitor. Modification of the steroid regimen may take into consideration possible confounders for the ALT elevation and impact on FVIII expression.

Unless otherwise indicated, treatment with reactive corticosteroids should be initiated at a dose of 60 mg per day and then gradually tapered if the ALT level remains stable or declines after 2 weeks (60 mg daily for the first 2 weeks, then 40 mg the next 2 weeks, then 30 mg the next two weeks, then 20 mg the next two weeks, then 15 mg for the next week, then 10 mg for the next week, then 5 mg for the next week, then stop, for a total treatment of 11 weeks) (refer to Table 9.1.6).

Should a scenario arise in which differences from the minimum recommended dose and/or duration of reactive corticosteroids may be clinically indicated, a discussion should take place between the Investigator and Medical Monitor regarding corticosteroid dose adjustments. Management of ALT elevations with reactive corticosteroids, including tapering of doses and managing worsening and/or recurrent ALT elevations, should be guided by the following (Table 9.4.8.2.1.1):

Table 9.4.8.2.1.1: Management of ALT Elevations with Reactive Corticosteroids

r	
	• Repeat LTs and FVIII within 24-72 hours
	• Continue to monitor LTs until ALT is stable or not increasing

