	• Investigate for alternative etiologies (eg, concomitant medications, viral or autoimmune hepatitis, alcohol use, recreational drug use, special diets, strenuous exercise, prior and/or concurrent illnesses, exposure to environmental and/or industrial chemicals, etc.)
	• If no alternative etiology is found, contact the Medical Monitor to discuss the initiation of reactive corticosteroids with the following tapering schedule: 60 mg x 2 weeks; 40 mg x 3 weeks; 30 mg x 1 week; 20 mg x 1 week; 10 mg x 1 week upon consultation with the Medical Monitor
$ALT \ge 1.5x$	• Consider evaluation with additional liver tests (including but not limited to ALT, AST, bilirubin, and alkaline phosphatase)
Baseline or > ULN	• Consider obtaining other possibly relevant laboratory evaluations (albumin, PT/INR, CRP, etc.)
	Consider obtaining complete blood count with differential to assess for eosinophilia
	• Consider obtaining PBMC, C3, C3a, Bb, and sC5b-9 to evaluate potential immune response (prior to starting reactive oral corticosteroids)
	• Continue to taper as long as subject's ALT is not increasing. Decisions regarding regimen modification may be made based upon Investigator judgement and discussion with the Medical Monitor
	• For any ALT elevations that begin after 52 weeks on study, please consult the Medical Monitor prior to initiating corticosteroids unless there is an imminent safety concern
	If after 2 weeks ALT levels have worsened with corticosteroid dose of 60 mg/day, the following is recommended:
	 Investigate for alternative etiologies including labs noted above, if not previously checked
Warraning ALT	 Increase corticosteroid dose up to a maximum of 1.2 mg/kg for no more than 2 weeks
Worsening ALT	• For subjects who are refractory to the maximum dose of corticosteroids, or intolerant to use of corticosteroids, consider use of alternative immunosuppressants (tacrolimus or mycophenolate)
	Consider gastroenterology and/or hepatology consult, abdominal workup, imaging (including MRI or ultrasound), and/or liver biopsy as appropriate Any concerns should be discussed between the Investigator and the Medical Monitor
Recurrent ALT elevations	If the subject has recurrent ALT elevations ($\geq 1.5x$ Baseline or $>$ ULN) and there are no safety concerns, the decision regarding management may be made at the discretion of the Investigator after discussion with the Medical Monitor

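### Amendment 10 gives two default tapers for reactive corticosteroids, 11 weeks and 8 weeks, and does not say which prevails

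*Protocol*

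**What the plan says.** All of the following is current Amendment 10 text.

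**Taper.** The text of Section 9.4.8.2.1 starts at 60 mg per day and steps down through 40, 30, 20, 15 and 10 mg, ending "then 5 mg for the next week, then stop, for a total treatment of 11 weeks". Table 9.1.6 shows the same course week by week, in eleven columns. The same section then says that management of ALT elevations, tapering included, should follow Table 9.4.8.2.1.1. The taper in that table is "60 mg x 2 weeks; 40 mg x 3 weeks; 30 mg x 1 week; 20 mg x 1 week", then one week at 10 mg, in consultation with the Medical Monitor. Footnote b of Table 9.1.6 sends the reader to Section 9.4.8.2 for tapering guidance, which leads to both versions.

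**ALT threshold.** The text says "In general, reactive corticosteroids may be initiated when a subject's ALT value is" at or above 1.5x ULN, or after review of FVIII and liver enzyme data in consultation. Table 9.1.6 footnote a ("Reactive corticosteroids may be initiated when a subject's ALT value is" at or above 1.5x ULN) agrees and carries the same consultation clause. The 30-minute report to the medical monitor (Section 9.4.8.2.1) and the event of special interest definition (Section 10.2.1) also use 1.5x ULN. The first row of Table 9.4.8.2.1.1 is labelled ALT at or above 1.5x "Baseline or > ULN", and the row on recurrent elevations uses the same definition.

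**Testing frequency.** Footnote b of Tables 9.1.2 to 9.1.4 allows flexible timing of liver tests, "but LTs will be monitored at least twice weekly during periods when a" subject's ALT is at or above 3x ULN. Footnote d of Table 9.1.6 says that, whatever those three tables list, "subjects initiated on corticosteroids will only be required to have laboratory evaluations on a weekly basis".

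**The concern.** A site that faces an ALT rise finds two complete dosing schedules in one section, each presented as the standard. No sentence ranks them. This is a safety pathway, and it is still in use: subjects are followed to Week 364, and Section 9.4.8.2.1 with its table expressly covers elevations that begin after Week 52. Two subjects with the same late rise could receive courses of different length, and neither course would be a protocol deviation.

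The thresholds add a second uncertainty. A rise that meets only the table's row enters the pathway towards a steroid discussion, yet it is neither a raised liver test for the 30-minute report nor an event of special interest.

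**Working it through.** **1. Reproduce the stated duration.** Text of Section 9.4.8.2.1: 2 + 2 + 2 + 2 + 1 + 1 + 1 = 11 weeks. This matches the stated total and the eleven columns of Table 9.1.6.

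**2. Duration in Table 9.4.8.2.1.1.** 2 + 3 + 1 + 1 + 1 = 8 weeks, with no step at 15 mg or 5 mg.

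**3. Cumulative dose** (daily dose x 7 days x weeks).
- Text and Table 9.1.6: 14 x (60 + 40 + 30 + 20) + 7 x (15 + 10 + 5) = 2100 + 210 = 2310 mg.
- Table 9.4.8.2.1.1: 14 x 60 + 21 x 40 + 7 x (30 + 20 + 10) = 840 + 840 + 420 = 2100 mg.
- Difference: 3 weeks and 210 mg, and 210/2310 = 9%.

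**4. Week by week (mg per day).**

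| Week | 1 | 2 | 3 | 4 | 5 | 6 | 7 | 8 | 9 | 10 | 11 |
|---|---|---|---|---|---|---|---|---|---|---|---|
| Text, Table 9.1.6 | 60 | 60 | 40 | 40 | 30 | 30 | 20 | 20 | 15 | 10 | 5 |
| Table 9.4.8.2.1.1 | 60 | 60 | 40 | 40 | 40 | 30 | 20 | 10 | 0 | 0 | 0 |

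The schedules differ in Weeks 5, 8, 9, 10 and 11.

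**5. Do the two tapers address the same subjects?** Any ALT at or above 1.5x ULN is also above ULN. So every subject who reaches the text's ALT threshold also falls in the table's first row. If no alternative cause is found, both tapers apply to him.

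**6. Thresholds, in multiples of ULN.** The text is met at 1.5. The table's row is met at the smaller of 1.5 x baseline and 1.0. The documents give no baseline ALT values, so these baselines are assumptions:

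| Assumed baseline (x ULN) | Table row met at | Text met at |
|---|---|---|
| 0.3 | 0.45 | 1.5 |
| 0.5 | 0.75 | 1.5 |
| 0.67 to 1.0 | about 1.0 | 1.5 |

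With an assumed ULN of 40 U/L and baseline of 20 U/L, that is 30 against 60 U/L. With a baseline near ULN it is about 40 against 60 U/L. Whatever the baseline, an ALT above ULN but below 1.5x ULN meets the row and not the text's numeric threshold.

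**7. Testing frequency.** For a subject on steroids with ALT at or above 3x ULN, footnote b requires at least two liver tests a week and footnote d one. The twice-weekly rule appears only in Tables 9.1.2 to 9.1.4, which cover Year 1. Footnote b of Table 9.1.5 (Years 2 to 7) does not carry it.

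**8. Timeline.** Section 24 of Amendment 10 (24 August 2021) records that Table 9.4.8.2.1.1 is new. Amendment 9 (19 June 2020) had only the 11-week taper and the 1.5x ULN threshold, and its summary of changes says recruitment was already complete. The second taper therefore appeared about 14 months after that statement.

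**The case against.** The strongest defence is that the protocol leaves room for judgement and puts a sponsor role in the loop. The text applies its course unless something else is indicated. The table ties its taper to consultation with the Medical Monitor, and for rises after 52 weeks asks for that consultation before steroids start unless safety is in imminent danger. This stands in part: different management is possible, not certain. It does not remove the conflict, because the Medical Monitor reads the same two schedules. Nor can the table simply be the exception to the text: by step 5 the exception would cover every subject who meets the text's ALT threshold, and Table 9.1.6 would still show 11 weeks.

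On the thresholds the defence is better. The table's row does not start steroids. It asks for repeat tests, a search for other causes and, if none is found, a discussion. The text's consultation clause permits a start below 1.5x ULN. The two can coexist; what is missing is a statement of how.

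On testing, footnote d opens as an override of exactly the tables that hold the twice-weekly rule, so it may be a deliberate precedence rule. Nothing says that relaxing the rule at high ALT was intended, but the question concerns Year 1 only.

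A reader might infer more than the documents support:

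- **That steroid exposure confounds FVIII or ALT comparisons between cohorts, or that past courses need sorting by rule.** Recruitment was complete, under one taper and one threshold, well before the second taper was written. The remark in Section 7.4 about corticosteroid regimens compares this study with 270-301, not sites or cohorts within this study.
- **That monitoring is halved for subjects now in follow-up.** The twice-weekly rule does not extend beyond Year 1.
- **That the step for worsening ALT, up to 1.2 mg/kg, contradicts the 60 mg start.** It is a cap, and it equals 60 mg only at 50 kg (1.2 x 50 = 60). No subject weights are given.
- **That the hepatitis re-tests must be re-timed.** They are set at 1 and 13 weeks after steroids end and so follow whichever course is given: Weeks 12 and 24, or 9 and 21, from the start.

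**Conclusion.** The taper contradiction is established from current text and needs no assumption: 11 weeks and 2310 mg against 8 weeks and 2100 mg, with different daily doses in five of eleven weeks and no rule of precedence. The difference in total dose is modest (9%); the differences in duration and in the last steps of the taper are what a site would notice. The practical reach is late ALT rises in subjects still in follow-up, who could be managed differently, subject to Medical Monitor consultation.

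The ALT thresholds are unclear in their relation rather than in direct conflict. The size of the gap depends on baseline ALT, which is assumed here. The testing-frequency discrepancy is real on paper but mainly historical. Which taper, threshold or testing rule is clinically right is not judged.

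**What to change.** Issue a clarification letter or short amendment that does three things:

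1. Reconciles the text of Section 9.4.8.2.1, Table 9.4.8.2.1.1 and Table 9.1.6 into one stated taper.
2. States how the table's ALT row, including its definition of recurrence, relates to the 1.5x ULN threshold in the text, Table 9.1.6 footnote a, the 30-minute report and the event of special interest definition.
3. States whether Table 9.1.6 footnote d is meant to override the twice-weekly rule in footnote b of Tables 9.1.2 to 9.1.4.

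The sponsor's medical monitor and hepatology advisers decide which rule stands. The cost is one document and its circulation to sites. No change to data collection or to the analysis is needed.

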9.4.9 Treatment Compliance

Study drug will be administered to subjects at the study site by a qualified professional. The quantity dispensed, returned, used, lost, etc. must be recorded on a dispensing log. Sites will be instructed to return or destroy all used and unused study drug containers.

Proprietary and Confidential

9.5 Investigational Product Accountability

The Investigator or designee is responsible for maintaining accurate records (including dates and quantities) of IP(s) received and IP lost or accidentally or deliberately destroyed. The Investigator or designee must retain all unused or expired study supplies until the study monitor (on-site CRA) has confirmed the accountability data, if allowed by local SOPs.

9.5.1 Return and Disposition of Clinical Supplies

Unused study drug must be kept in a secure location for accountability and reconciliation by the study monitor. The Investigator or designee must provide an explanation for any destroyed or missing study drug or study materials (or must be referenced in their institution SOPs).

Unused study drug may be destroyed on site, per the site's standard operating procedures, but only after BioMarin has granted approval for drug destruction. The monitor must account for all study drug in a formal reconciliation process prior to study drug destruction. All study drug destroyed on site must be documented. Documentation must be provided to BioMarin and retained in the Investigator study files. If a site is unable to destroy study drug appropriately, the site can return unused study drug to BioMarin upon request. The return of study drug or study drug materials must be accounted for on a study drug return form provided by BioMarin.

All study drug and related materials should be stored, inventoried, reconciled, and destroyed or returned according to applicable state and federal regulations and study procedures.

9.6 Dietary or Other Protocol Restrictions

There are no dietary or other protocol restrictions for this study.

Subjects should be advised to abstain from any blood or sperm donation after BMN 270 infusion, until there is no further evidence of vector shedding from PCR analysis of samples.

9.7 Safety and Efficacy Variables

As this is a first-in-man study, the primary endpoint of safety will be assessed as explained in Section 9.7.9.

The primary efficacy measure will be to assess plasma FVIII activity. The efficacy goal of the study is to establish the dose relationship to FVIII activity \geq 5 IU/dL at 16 weeks post BMN 270 administration.

9.7.1 Safety and Efficacy Measurements Assessed

The Schedule of Events (Table 9.1.1 through Table 9.1.5) describes the timing of required evaluations.

9.7.2 Primary Efficacy Variables

The primary efficacy measure will be the plasma FVIII activity monitored on a regular basis after BMN 270 dose. The efficacy goal of the protocol is to ascertain the dose range of BMN 270 required to convert severe HA patients to expression of FVIII at 5 IU/dL or above, (ie, a mild severity). This is associated in natural history studies with clinically superior long term outcomes (Den Ujil 2011).

The following assays (assessed by the central laboratory) will be used to measure the primary efficacy variable:

- FVIII activity (chromogenic substrate assay)
- FVIII activity by one-stage clotting assay

If a subject has used FVIII within 72 hours of a measurement day, all efforts should be made to obtain FVIII activity measurements when a 72-hour interval without FVIII use is achieved. The 72-hour wash-out period is only intended for subjects who have achieved FVIII ≥ 5 IU/dL at 16 weeks after BMN 270 infusion and who have not resumed standard of care FVIII replacement therapy.

The FVIII activity level in both assays and the number of subjects with FVIII activity ≥ 5 IU/dL in at least one of the two assays will be summarized.

FVIII activity assays will also be performed at the local laboratory at the time points indicated in Table 9.1.2, Table 9.1.3, Table 9.1.4, and Table 9.1.5 but will be used in conjunction with local lab LT assessments to monitor subject safety and need for initiation of reactive corticosteroid dosing; local laboratory FVIII activity assessments will not be used to assess efficacy or to measure the primary efficacy outcome of the study.

Subjects who do not respond to BMN 270 treatment (ie, treatment failure, manifesting as failure to achieve FVIII activity ≥ 5 IU/dL by Week 52 and inability to maintain independence from prophylactic FVIII replacement therapy due to joint bleeding episodes, in the judgment of the Investigator) may, at the Investigator's discretion and after discussion with the Medical Monitor, follow an abbreviated visit schedule after Week 52, as applicable and at the discretion of the Investigator.

Timing of assessment by these assays is provided in Table 9.1.2, Table 9.1.3, Table 9.1.4, and Table 9.1.5. Details on performing the assays are included in the Laboratory Manual.

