7 INTRODUCTION

Haemophilia A (HA) is an X-linked recessive bleeding disorder that affects approximately 1 in 5,000 males (Iorio 2019). It is caused by mutations in the factor VIII (FVIII) gene that codes for FVIII protein, an essential cofactor in the coagulation cascade. Clinical manifestations of severe FVIII deficiency are frequent unprovoked bleeding episodes in joints and soft tissues causing permanent disability and occasionally death mostly after brain haemorrhage. Treatment in Western (Berntorp 2012) countries consists of intravenous injection of plasma derived or recombinant FVIII protein concentrates at the time of a bleed, or prophylactically, to prevent bleeding episodes. The short half-life for FVIII (~8-12 hours) necessitates frequent infusions and makes this treatment prohibitively expensive for the majority of the world's haemophilia A patients. These individuals develop debilitating arthropathy and have a substantially increased risk of death from haemorrhage in life (Stonebraker 2010). Chemical modification or bioengineering of FVIII may improve half-life to 18-19 hours (Kaufman 2013). However, these long acting FVIII variants do not eliminate the need for lifelong FVIII protein administration (Hay 2012).

Gene therapy offers the potential of disease-modifying therapy by continuous endogenous production of human FVIII following a single administration of vector. Haemophilia A is well suited for this approach because its clinical manifestations are attributable to the lack of a single gene product (FVIII) that circulates in low amounts (100-200 ng/ml) in the plasma. Tightly regulated control of gene expression is not essential and a modest increase in the level of FVIII (a plasma level of 2 ng/ml protein leads to a 1% expression) can ameliorate the severe phenotype (Srivastava 2020); thus the therapeutic goal for gene therapy is a modest increase in hFVIII. Finally, the consequences of gene transfer can be assessed using simple quantitative rather than qualitative endpoints that can be easily assayed in most clinical laboratories.

BMN 270 contains the cDNA for the B-domain deleted SQ FVIII with a liver-specific HLP transcription promoter. The expression cassette is inserted between AAV2 ITRs and this genome is packaged in the AAV5 capsid. A comprehensive review of BMN 270 is contained in the IB supplied by BioMarin. Investigators are to review this document prior to initiating this study.

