7.3 Study Rationale

Haemophilia A (HA) is an X-linked recessive bleeding disorder that affects approximately 1 in 5,000 males (Iorio 2019). It is caused by deficiency in the activity of coagulation factor VIII (FVIII), an essential cofactor in the intrinsic coagulation cascade. This disorder can be either inherited, due to a new mutation or an acquired immunologic process, leading to insufficient quantities of FVIII or a dysfunctional FVIII, but all are characterized by a defective coagulation process. The clinical phenotype of HA patients is largely governed by the level of residual expression. Severe HA is classified as FVIII activity less than 1% of wild type (< 1 IU/dL), moderate disease comprises 1-5% of wild type activity and the mild form is 5-40% activity. The clinical manifestations of severe HA remain frequent spontaneous bleeding episodes, predominantly in joints and soft tissues, with a substantially increased risk of death from haemorrhage when the brain is involved.

Treatment of severe HA presently consists of intravenous injection of plasma derived or recombinant human FVIII protein (rhFVIII) concentrates both as prophylaxis 2-4 times per week, and at the time of a bleed, to prevent or control bleeding episodes, respectively. The half-life for FVIII (12-18 hours for most approved products) necessitates frequent infusions, and although a major advance in the treatment of HA, it remains common for severe HA patients to continue to have multiple bleeding events on treatment (mean of 1 to 7 episodes/year with prophylaxis and up to 30 to 50 episodes/year for on demand treatment) (Nagel 2011). The consequence of multiple bleeding events is the development of an underlying pathology that contributes to debilitating multiple-joint arthropathy and

270-201 Amendment 10

[figure not shown]
Page 31

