14.1.2 Procedures for Accounting for Missing, Unused and Spurious Data

Missing data will not be imputed.

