14.2 Primary and Secondary Efficacy Analysis

The subjects will be followed in a longitudinal manner and all the relevant information will be collected. The analysis of the data will be descriptive in nature. Descriptive statistics include the number of subjects, mean, median, standard deviation, minimum, and maximum for continuous variables and count and percent for categorical variables. Efficacy variables will be summarized by dose cohort at each time point. Relationship between dose and efficacy results will be examined.

Data collected in a longitudinal manner may be analyzed using longitudinal methods such as mixed effect model which takes into account the correlation among the observation taken at various time points within a participant. Efficacy is a secondary endpoint, defined as biologically active hFVIII at ≥ 5 IU/dL by chromogenic substrate assay and/or one-stage clotting assay as measured by the central laboratory at 16 weeks following study treatment. We can only assess the true steady state of hFVIII protein produced from BMN 270 after a minimum of 72 hours has elapsed since the last infusion of FVIII protein concentrates.

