14.7 Determination of Sample Size

No formal sample size calculations based on statistical power were performed.

The sample size is determined based upon clinical consideration and could detect a strong clinical efficacy signal. Up to 15 subjects may be dosed in the study; the actual number of subjects will depend on the criteria for dose escalation.

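### The 72-hour washout is tied to having already reached 5 IU/dL at Week 16, which conflicts with Section 14.2 and lets injected FVIII be counted as expression

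*Protocol*

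**What the plan says.** Section 9.7.2 opens with a general best-efforts instruction: "If a subject has used FVIII within 72 hours of a measurement day, all efforts should be made to obtain FVIII activity measurements" after a 72-hour interval without FVIII. The next sentence narrows it: "The 72-hour wash-out period is only intended for subjects who have achieved FVIII ≥ 5 IU/dL at 16 weeks after BMN 270 infusion". A second condition in that sentence leaves out anyone already back on standard replacement. The same pair of sentences is attached to the Day 4 and Weeks 1-16 draws (Sections 12.5.1 and 12.5.2, Table 9.1.2 footnotes) and to the later visits through Year 7 and early termination.

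Section 14.2 states the validity condition with no exception by responder status: "We can only assess the true steady state of hFVIII protein produced from BMN 270 after a minimum of 72 hours has elapsed". The interval is counted from the most recent concentrate infusion.

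The responder count in Section 9.7.2 is the number of subjects at or above 5 IU/dL in either of the two central assays. It carries no condition on time since infusion. Section 9.4.8.1 stops prophylaxis on the day of vector infusion but lets subjects take FVIII whenever needed. Sections 9.1 and 9.7.3 foresee that prophylaxis may be resumed. On gaps in the data, Section 14.1.2 says only: "Missing data will not be imputed".

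**The concern.** Whether a Week 16 value is collected after washout depends on what that value turns out to be, so the rule is circular at the visit that defines efficacy. Before Week 16 nobody's status is known, yet the same note governs those draws, including the Week 3 reading used for escalation. After Week 16 the washout does not apply to subjects below 5 IU/dL or back on replacement, who are the likeliest to have FVIII concentrate in their plasma.

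The error can run only upwards. A truly low subject may be lifted over 5 IU/dL at Week 16, and cohort means in Years 2-7 may be held up by subjects who have lost expression and resumed FVIII. Treatment failure is also exposed: it requires both failure to reach 5 IU/dL by Week 52 and inability to stay off prophylaxis. Subjects who meet the second condition are exempt from washout, so the first may be judged on injected FVIII.

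**Working it through.** The protocol gives no numerical figure to reproduce here. The study is descriptive (Section 14.7: "No formal sample size calculations based on statistical power were performed"). The check sets the passages side by side and then sizes the possible contamination.

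**Who has a washout condition, and when**

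| Situation | Section 9.7.2 and visit notes | Section 14.2 |
|---|---|---|
| Before Week 16 | Cannot be determined | 72 h needed |
| At Week 16 | Depends on the value being measured | 72 h needed |
| Later, at least 5 IU/dL at Week 16, off replacement | Washout intended | 72 h needed |
| Later, below 5 IU/dL at Week 16 or back on replacement | No washout | 72 h needed |

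The columns agree in one row of four.

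**Residual from one infusion**

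Inputs: half-lives of about 8-12 h (Section 7), 12-18 h (Section 7.3: "The half-life for FVIII (12-18 hours for most approved products) necessitates frequent infusions") and 18-19 h for modified products (Section 7: "Chemical modification or bioengineering of FVIII may improve half-life to 18-19 hours"). The protocol gives no FVIII dose or recovery, so the peak rise is an assumption, taken as 20-100 IU/dL.

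Formula: residual at time t = peak × 2^(−t / half-life). For a 12 h half-life at 24 h this is 20 × 2^(−2) = 5.0 and 100 × 2^(−2) = 25.0.

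| Half-life | 24 h (IU/dL) | 48 h (IU/dL) | 72 h (IU/dL) | Hours to fall to 5 IU/dL |
|---|---|---|---|---|
| 8 h | 2.5-12.5 | 0.3-1.6 | 0.04-0.20 | 16-35 |
| 12 h | 5.0-25.0 | 1.25-6.25 | 0.31-1.56 | 24-52 |
| 18 h | 7.9-39.7 | 3.2-15.8 | 1.25-6.25 | 36-78 |
| 19 h | 8.3-41.7 | 3.5-17.4 | 1.45-7.23 | 38-82 |

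Within 24 h, one infusion can reach the 5 IU/dL threshold with no vector expression at all. At 72 h the residual is below 5 IU/dL at 8 and 12 h. At 18-19 h it stays above only for large rises: 5 / 2^(−72/18) = 80 IU/dL and 5 / 2^(−72/19) = 69 IU/dL.

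**Effect on a cohort**

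One misclassified subject moves the responder rate by 1/6 = 17 points in a cohort of 6 (Cohort 4 after expansion) and 1/4 = 25 points in a cohort of 4 (the planned maximum in Cohorts 1-3).

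**Effect of merely dropping contaminated values later**

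Assumed illustration: of six subjects, four are truly at 50 IU/dL and two are truly at 1 but read 15 on prophylaxis.
- True mean: (4 × 50 + 2 × 1) / 6 = 33.7
- Contaminated mean: (4 × 50 + 2 × 15) / 6 = 38.3
- Mean after dropping the two: 50

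With no imputation, exclusion alone makes the durability bias worse.

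**The case against.** The strongest defence is that the restriction tells sites whom to sample after washout, and was probably meant to spare subjects who need replacement. Section 14.2 already says what can be interpreted, and excluding contaminated samples is ordinary SAP content. The SAP was not available, and under Section 14.9 it prevails over the protocol. This stands against one tempting inference, that injected FVIII is in fact counted as expression: no passage says so. It does not remove the conflict. The protocol itself fixes who is sampled after washout, and a SAP cannot recover clean samples that were never sought.

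A reader might also infer that the non-responders are exactly the subjects affected. They are not. A subject reading below 5 IU/dL despite residual FVIII is classified correctly at Week 16, and the exemption also covers responders who resumed replacement.

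Larger figures can be produced. With a 50 IU/dL rise every 56 h, a zero expresser stays at or above 5 IU/dL for 40 of 56 h (71%) at a 12 h half-life and throughout at 18 h. Those figures assume regular prophylaxis, which Section 9.4.8.1 stops at vector infusion, and a rise that the protocol does not give. They apply only to someone already back on prophylaxis. Nor do the documents support calling 72 hours too short in general, since that needs a rise of about 69-80 IU/dL or more with an 18-19 h product.

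Two limits on importance also stand. Section 14.2 treats efficacy as secondary and descriptive, and Section 7.4 reports most 6E13 vg/kg subjects above 50 IU/dL at Week 52, so a few IU/dL are unlikely to change that cohort's answer.

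**Conclusion.** The point holds as an internal contradiction with a badly fixed rule. Section 9.7.2 and the visit notes make the washout depend on the outcome, Section 14.2 requires it for everyone, and the responder count requires nothing. Exogenous FVIII can therefore be counted as expression in a truly low subject at Week 16 and in later summaries.

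The size is material against a 5 IU/dL threshold in cohorts of 4 to 6, but how often it happens cannot be known from the protocol. The residuals assume mono-exponential decay and a peak rise of 20-100 IU/dL; the half-lives are the protocol's own. The Amendment 9 rationale says recruitment is complete, so what can still be corrected is the reporting of Week 16 and durability. Past escalation decisions are not affected.

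**What to change.** Reconcile Section 9.7.2, Section 14.2 and the visit notes with one analysis rule for every subject and visit. It governs which measurements are evaluable and leaves clinical use of FVIII as it is.

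- **Evaluability.** Using the recorded infusion dates, a central FVIII value drawn within 72 h of exogenous FVIII is not evaluable as expression and cannot count toward 5 IU/dL.
- **Week 16.** The denominator is all dosed subjects in the cohort. A subject with no evaluable value counts as not shown to reach 5 IU/dL. A valid washed-out value of at least 5 IU/dL stands even if FVIII was later resumed.
- **Years 2-7.** Do not simply drop unevaluable values. Report the proportion of all dosed subjects with an evaluable value of at least 5 IU/dL. Beside each mean, show how many are unevaluable or back on prophylaxis. Add a sensitivity mean that sets those subjects to their pre-treatment FVIII level.
- **Longer-acting products.** A longer interval for 18-19 h products can be a sensitivity analysis.

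The cost is wording and some programming, and the counts may become slightly less favourable. A Week 16 rule written now is post hoc and should be labelled so.
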